Hypothesis 3: Better Treatment Attendance. Integrated clients will attend more behavioral therapy sessions and medication management sessions than Behavioral Only clients.

Hypothesis 4: Greater Medication Acceptance and Treatment Satisfaction. Integrated clients will more often consent to medication, show greater medication compliance, and report greater overall satisfaction than Behavioral Only.

Aim 3: Examine Patient-Centered Outcomes

Research Question 1: Heterogeneity of Treatment Effects. Will clients with co-occurring substance use problems have worse treatment outcomes than those without? Will there be outcome differences based on age, ethnicity, sex?

Research Question 2: Analysis of Individual Differences. Across treatment conditions, will clients who choose to start a medication regimen have better treatment outcomes than those who do not?

Study Design

This study emphasizes ecological validity: Both protocols will be implemented in existing outpatient behavioral services by agency clinicians. To promote internal validity, randomization will occur within site at both the client and therapist level (i.e., study therapists at

each site will be randomly assigned to condition). The primary benefit of “doubly randomized” designs is that they minimize potential bias related to site effects—because randomization occurs within each site—and therapist sampling bias—because therapists are randomly assigned to condition. The use of a Behavioral Only condition will control treatment expectancy effects. Therapists will be trained and supervised to implement CASH-AA and MIP as part of their otherwise routine duties; that is, the protocols will be additional components of their usual practice for study cases. To maximize protocol exposure, and to promote consistency in the timing of protocol implementation across conditions and cases, therapists will be asked to implement CASH-AA and MIP at the start of treatment (unless contraindicated).

Note: (1) ADHD medication will be available to all Behavioral Only cases via routine site practices for ADHD treatment; and (2) MIP supports family decision-making about medication but does not require families to start a medication regimen.

Sample Description

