measure. Also, phone screening data from the engaged versus non-engaged samples will be compared to test for significant differences in demographic or family characteristics.

Analytic Strategy to Account for Nesting Effects

The proposed study has a nested design: clients are nested within therapists, and therapists are nested within treatment sites. In a nested design, the application of a standard fixed effects GLM typically produces biased inferential tests because the error terms of units within each level are often correlated. We will use multilevel modeling with random effects that includes the sandwich estimator to adjust parameter estimates and standard errors for nested structure. This approach is used to analyze nested data when the goal is to examine outcome effects at the level of the individual (i.e., client), and the hierarchical structure of the data (i.e., client nesting at therapist level) is akin to a nuisance factor to be accounted for, but inference about the degree of correlation is not of interest. Also, the design is nested at the level of treatment site: therapists are nested within site. Recommendations stipulate that 10-20 sites are needed to produce stable estimates for random effects modeling. Because this study will include only four sites, we will adopt the typical alternative of modeling site as a fixed effect included as a nuisance covariate in analyses. This approach is the norm for multisite studies in behavioral sciences whenever there is a small number of participating sites. If the fixed effect of treatment site is significant for any given client outcome analysis, we will re-conduct the given analysis using a within-site approach; due to small sample size this would be considered an exploratory analysis.

Plan of Analysis for Main Outcomes: Aims 1 & 3

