LGC will proceed using Mplus version 7, as follows. First, we will test a series of growth curve models for each outcome, representing three forms of growth (no change, linear change, quadratic change), to determine the overall shape of the individual change trajectories; overall model fit will be evaluated by examining the chi-square, RMSEA, CFI, and TLI indices. Second, we will test unconditional models for all outcomes to obtain the average effect for change over time in outcome, without including treatment condition or other covariates. Third, we will add the two predictors, Condition (Behavioral Only vs. Integrated) and baseline Substance Use (SU+ vs. SU-) to the models in order to test the impact of each predictor on initial status and change over time. We will also test Condition X SU interactions, and if any are significant for a given outcome, we will re-run that model separately for the SU+ and SU- participants to test simple effects. Treatment effects (Aim 1) for any given outcome will be shown by a statistically significant effect parameter, as tested by the pseudo z test—calculated by dividing the coefficient by its standard error—associated with Condition. Heterogeneity of Treatment Effects (HTE; Aim 3) for any given outcome will be identified by a significant effect for the Condition X SU interaction term; post-hoc analyses will be used to explore these interactions to determine whether Integrated effects appeared to be stronger or weaker in SU+ versus SU- cases. Initially, all models will be adjusted for nuisance covariates: sex, age, and ethnicity; family income; caregiver education level; and treatment site. We will then further explore HTE (Research Question 1) by testing for outcome differences based on age, ethnicity, and sex subgroups. Per above we will use the sandwich estimator to control for therapist nesting. Effect size estimates for significant findings in Aims 1 and 3 analyses will be calculated based on Feingold's procedures for calculating effect sizes for LGC analyses. Also, for any outcome that deviates substantially from normality—typical for delinquency and SU data—we will use two-part growth curve models, which allow for the simultaneous estimation of separate but correlated continuous and categorical LGC models. Two-part models are used when a large number of participants report the absence of the given variable (i.e., no delinquent activities or SU), resulting in highly skewed data. In two-part models, the original distribution of the outcome is separated into categorical and continuous parts, each modeled by separate but correlated growth functions. In the categorical part, a binary indicator variable is created to indicate any vs. none of the outcome in question. The continuous part models the frequency of occurrence of the outcome given any positive occurrence.

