
Finally, for Research Question 2 pertaining to Individual Differences, we will use methods in which days of ADHD medication use since study entry is positioned as a predictor of client outcomes. Because medication use will be dependent on client choice and not randomly assigned, the first step is to create 2 new groups: High Use vs. Low/No Use (or 3 groups, depending on data distributions). This will be done via propensity score matching analyses for ordinal treatment variables. Propensity scores will be calculated using an ordinal logit model to represent each client's probability to be medicated over time as a function of multiple baseline variables presumed to influence medication choice (condition, demographics, ADHD symptom severity, comorbid symptoms). Clients will be matched on these variables to minimize differences in propensity scores and maximize differences in medication use days at 12-month FU. This will statistically control for observed variables that might influence the likelihood of natural selection into medication use over time. Once propensity score-based groups are created, we will conduct matched-pair analyses for each outcome, using dependent *t*-tests for continuous and McNemar's chi-square test for dichotomous variables⁷⁸.

Plan of Analysis for Main Outcomes: Aim 2

Multilevel modeling will examine Condition effects on time-invariant client outcomes: treatment attendance, medication acceptance, and client satisfaction (averaged across caregiver and adolescent); separate models will be run for each variable. Outcomes will be analyzed using multilevel regression analysis with random intercepts and slopes in Mplus version 7. Condition will be entered as a level-1 predictor and regressed directly on the outcome variable; the influence of the predictor is examined by testing the significance of the effect parameter. As discussed above, to control for therapist nesting effects we will use the sandwich estimator; all models will be adjusted for the nuisance covariates listed above; and missing data will be handled with robust maximum likelihood estimation (see below).

Analytic Plans for Missing Data

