Note also that the FDA mandates that a “black box” warning label be affixed to bottles of several brands of stimulants that contains the following consumer safety information: (1) chronic abusive use can lead to marked tolerance and psychological dependence with varying degrees of abnormal behavior; (2) frank psychotic episodes can occur, especially with abusive use; (3) should be given cautiously to patients with a personal or family history of drug dependence or alcoholism; (4) careful supervision given during drug withdrawal from abusive use since severe depression may occur; (5) withdrawal during chronic therapeutic use may unmask symptoms of the underlying disorder that may require follow-up. In addition, the FDA recommends caution in treating patients whose underlying medical conditions might be compromised by increases in blood pressure or heart rate, for example, those with preexisting hypertension, heart failure, recent myocardial infarction, or hyperthyroidism, or those already using vasopressor agents. There are additional cautions related to taking long-acting, osmotic-release medication (OROS-MPH, aka Concerta): (1) If not taken early in the morning, doctors often recommend skipping the dose for that day, as the stimulants will affect normal sleep patterns. (2) Some people find that even with early morning dosing, stimulants disrupt normal sleep patterns. (3) Changing the dosage by any amount requires a new prescription.

Potential Risks for Therapist Participants

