Medication needs assessment, dosage monitoring, and tolerance and effectiveness monitoring will be conducted at the respective partnering treatment sites by an on-site psychiatrist as part of routine child psychiatric services provided during the course of behavioral health counseling. All partnering sites are licensed to provide pharmacological interventions for youth with mental health disorders, and all operate in compliance with state-mandated safety monitoring and adverse event protocols, in addition to safety and best practice guidelines put forth by the American Psychiatric Association, in the dispensation of pharmacological services for minors. Prior to prescribing medication, site psychiatrists will carefully review all safety information and precautions (including information contained on FDA black box warning labels) with both the adolescent and primary caregiver(s), and the psychiatrist will conduct all assessment procedures necessary to determine whether medication is indicated and safe to prescribe for a given client. If medication is ultimately prescribed and accepted, site psychiatrists will meet on a regular basis with adolescents and families for medication titration and management, per routine site procedures. Medication management will be coordinated with the site behavioral clinicians throughout the course of treatment. Any adverse events (AEs) or serious adverse events (SAEs) related to medication interventions will be clinically managed by

site psychiatrists, including toxicity assessment, downward titration, termination of the medication regimen, and emergency treatment or hospitalization as indicated. Any AEs/SAEs that occur at any treatment site will be reported directly to the CASAColumbia IRB by the Principal Investigator per established institutional protocols.

Protection Against Study Risks for Therapists

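### The Research Question 2 propensity list omits treatment site, so clinic differences could be counted as medication effects if sites differ in both medication use and outcome

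*Combined protocol and SAP*

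**What the plan says.** The Research Question 2 text is in Data Analysis, Plan of Analysis for Main Outcomes: Aims 1 & 3. Medication use is the client's choice, so an ordinal logit propensity model is fitted to "multiple baseline variables presumed to influence medication choice (condition, demographics, ADHD symptom severity, comorbid symptoms"). The list has no qualifier such as 'for example', and site is not named. Then: "Clients will be matched on these variables to minimize differences in propensity scores and maximize differences in medication use days at 12-month FU". The outcome step is: "we will conduct matched-pair analyses for each outcome, using dependent *t*-tests for continuous and McNemar's chi-square test for dichotomous variables".

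Other sections bear on site:

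- Analytic Strategy to Account for Nesting Effects commits to "modeling site as a fixed effect included as a nuisance covariate in analyses". It adds an exploratory within-site re-analysis where the site effect is significant.
- The growth models are adjusted for covariates ending in "family income; caregiver education level; and treatment site". The Aim 2 paragraph carries the same covariates over explicitly; the Research Question 2 paragraph does not.
- The Study Design note says "ADHD medication will be available to all Behavioral Only cases via routine site practices for ADHD treatment". The section on protection against medication risks has site psychiatrists meeting families "for medication titration and management, per routine site procedures".
- Under Linking to treatment, families reach a site by capacity, proximity or that site's own referral stream, not by randomisation.

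**The concern.** A variable that affects both medication days and outcome confounds this comparison. Site is a candidate on both counts. The protocol routes prescribing, titration and follow-up through each clinic, and it treats site as something the other outcome models must adjust for. Because clinics draw families non-randomly, their clienteles and results may differ.

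With site outside the propensity model, a high user from one clinic can be paired with a low user from another. A dependent t-test or McNemar's test cannot then adjust for site, so the general site rule can reach this analysis only through the matching. At stake is the answer to whether clients who take medication do better, which the Project Abstract says the study will assess.

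**Working it through.** The plan states no power, effect size or expected medication rate for Research Question 2, so there is no figure to reproduce. What follows illustrates size on assumed inputs.

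**Inputs from the documents.** 140 randomised. Four sites (Study Purpose and Aims; nesting section), although the Project Abstract says three. Missing outcome data 10-15%, so at the upper end 140 × 0.85 = 119 analysed.

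**Assumed.** True medication effect zero, equal-sized sites, within-site SD of 1, equally spaced site values, pairs formed without regard to site.

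**Formula.** Spurious effect = sum over sites of [P(site | High Use) − P(site | Low/No Use)] × site outcome mean.

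**High-use rates 20% to 40%** (0.200, 0.267, 0.333, 0.400; sum 1.20, complements 2.80).
- Shares of high users: 0.167, 0.222, 0.278, 0.333.
- Shares of low users: 0.286, 0.262, 0.238, 0.214.
- Differences: −0.119, −0.040, 0.040, 0.119.
- Site means with SD 0.2: −0.268, −0.089, 0.089, 0.268.
- Effect: 2 × (0.119 × 0.268 + 0.040 × 0.089) = 0.07 SD. With site SD 0.4 it doubles to 0.14.

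**High-use rates 10% to 55%** (0.10, 0.25, 0.40, 0.55; sum 1.30, complements 2.70).
- Differences: −0.256, −0.085, 0.085, 0.256.
- Effect: 2 × (0.256 × 0.268 + 0.085 × 0.089) = 0.15 SD. With site SD 0.4 it is 0.31.

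The closed form thus gives 0.07-0.31 SD. Allowing for simulated matching, the range is roughly 0.07-0.33 SD.

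**A second grid** uses 119 clients and 4,000 simulated trials per cell. It shows the spurious effect in SD and the type I error of a two-sided 5% paired t-test:

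| High-use rates by site | Site means span 0.3 SD | 0.6 SD | 1.0 SD |
|---|---|---|---|
| 0.30-0.50 | 0.03; 5.6% | 0.07; 6.3% | 0.12; 8.0% |
| 0.20-0.60 | 0.07; 6.8% | 0.14; 9.8% | 0.23; 18.9% |
| 0.10-0.70 | 0.10; 8.1% | 0.21; 16.6% | 0.35; 35.0% |

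If sites differ only in use, or only in outcome, the effect is 0 and the error about 5%. All cells align higher use with better outcome; the reverse alignment reverses the sign.

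**Checking the remedies** (119 clients, four sites, no medication effect, optimal 1:1 matching without a caliper). In the settings where the listed covariates also confound, three covariates each act on outcome (0.25 SD) and on use (log-odds 0.5).
- Adding site to the propensity model cut the bias wherever site use rates differed: from 0.14 to 0.05 SD in one setting, and from 0.39 to 0.25 SD with rates of 10-55% and site SD 0.4.
- Forcing same-site pairs removes the site part but worsens balance on the other covariates. When those confound, 0.14-0.18 SD remains.
- With equal use rates, same-site pairing is slightly worse than pooled matching (0.13-0.14 against 0.10-0.11). With rates of 20-40% and site SD 0.2 the two are close (0.15 against 0.17). With rates of 10-55% and site SD 0.4 it clearly helps (0.17 against 0.40).

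**The case against.** The strongest reply is that site is already covered. The nesting section speaks of analyses generally, and the sentence adjusting all models for site stands under the same Aims 1 & 3 heading. The propensity list also names classes of variable rather than a full specification. This has some force as a reason to ask how the rule applies, but it does not settle the matter. The covariate sentence concerns the growth models, Research Question 2 names its own variables, and its paired tests have no site term. Site is not naturally a demographic either, since the growth-model list names it separately.

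Three further objections stand.

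- A reader might infer that clinic differences will be counted as medication effects. The documents do not support that. They give no medication rates or outcomes by site, and the nesting section calls site a nuisance covariate without asserting that it predicts outcome. Matching on demographics, severity and comorbidity would also remove part of any difference in clientele.
- A reader might infer that mandatory same-site pairs cure the problem at little cost. The check above shows a trade-off instead.
- A reader might want family history of drug dependence added as well, because the medication-risk section says stimulants "should be given cautiously to patients with a personal or family history of drug dependence or alcoholism" and the CASI-A collects family drug-use history. That wording is general label text, one of many cautions listed. The plan does not name it as a determinant of medication choice in this trial, and nothing ties it to outcome here.

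The simulations also simplify the planned method. They use two groups and 1:1 pairs, where the plan has an ordinal model, possibly three groups, and matching that also maximises differences in medication days.

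**Conclusion.** The omission is real on the text, and no later step in Research Question 2 repairs it. Its consequence is conditional: both medication use and outcome must differ by site after matching. Under the assumed rates (20-40% to 10-55%) and site outcome SD (0.2-0.4, same order), the spurious effect from site is roughly 0.07-0.33 SD. With milder differences it is small, and with a difference in only one of the two it is zero. These sizes rest wholly on assumed site figures.

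Research Question 2 is a non-randomised, exploratory question without a stated hypothesis. The randomised Condition comparison is untouched. The point merits a cheap change to the analysis text.

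**What to change.** In the Research Question 2 paragraph:

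1. Add treatment site to the propensity model variables.
2. Report balance after matching, by site and on each listed covariate.
3. Use same-site pairing only as a sensitivity analysis, or where balance on the listed covariates is kept.
4. State how the general site rule in the nesting section applies to this analysis, and reconcile the number of sites (three or four).

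The cost is a few lines of text; site is known for every randomised client. The downside is slightly poorer balance on the other covariates or, if a caliper is used, fewer pairs: about 2-10 fewer than pooled caliper matching in the assumed settings.

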The proposed study will help fill this alarming gap in the evidence base for adolescents with ADHD. The study is significant for several reasons. It will occur in existing behavioral health clinics to test front-line treatment effectiveness. Both protocols (CASH-AA and MIP) are evidence-based, affording a rigorous test of the best available treatment options for this clinical group. The test has immediate real-world implications: Families enrolled in specialty treatment settings invariably prefer behavioral services only, but they need to know whether integrated medication interventions can provide a meaningful boost to outcomes that are most important to them. Importantly, whereas ethnic minorities and also girls with are severely underserved and under-researched, the current study will focus on urban minority teens, and about half the sample will be female. Also, this study will be among the first to test evidence-based ADHD treatment options for adolescents who use substances, another significantly underserved and high-priority clinical risk group.

This comparative trial will randomly assign 140 adolescents with ADHD to Behavioral Only (containing CASH-AA) or Integrated (containing CASH-AA + MIP) treatment. The CASH-AA and MIP protocols will be incorporated in existing services in four clinics that support both study conditions. Adolescents and caregivers will complete research interviews at baseline and 3, 6, and 12-months follow-up. Multilevel modeling will compare conditions on symptom, quality of life, and service use outcomes and also test patient-centered heterogeneity of treatment effects and individual difference effects. Semi-structured interviews will document

family-specific rationale for decisions about initiating and continuing in behavioral and medication interventions, along with suggestions for improving the respective treatment services. The study has three specific aims:

Aim 1: Comparative Impact on Client Functioning

Hypothesis 1: Reduced Symptoms. Integrated clients will show greater decreases in ADHD symptoms (inattention, hyperactivity/impulsivity) and comorbid problems (conduct problems, drug use) than Behavioral Only clients.

Hypothesis 2: Improved Quality of Life. Integrated clients will show greater improvements in executive functioning (self-regulation, self-organization) and school functioning (grades, attendance, motivation) than Behavioral Only.

Aim 2: Comparative Impact on Service Utilization

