Based on 20 years of experience engaging high-risk adolescents and their families into longitudinal research, we expect to have rates of missing assessment data on outcome variables between 10-15%. All proposed analyses involving client outcome data will be carried out in Mplus, which provides full information maximum likelihood estimation (MLE), which produces unbiased parameter estimates under the assumption that data are missing at random. Moreover,

MLE outperforms other missing data approaches, such as listwise deletion, even when MAR is not met.

Risks And Benefits

Potential Study Risks

Potential Risks for Client Participants: Research Interviews and Treatment Session Recording

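### The matched-pair tests for Research Question 2 conflict with the plan's own missing-data and nesting rules, and the listed propensity variables omit baseline executive and school functioning

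*Combined protocol and SAP*

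**What the plan says.** The plan for Research Question 2 closes the section Plan of Analysis for Main Outcomes: Aims 1 & 3. Days of medication use since study entry define two use groups, or three if the data suggest it. Clients are matched on a propensity score modelled "as a function of multiple baseline variables presumed to influence medication choice (condition, demographics, ADHD symptom severity, comorbid symptoms"). The outcome step then reads: "Once propensity score-based groups are created, we will conduct matched-pair analyses for each outcome", "using dependent *t*-tests for continuous and McNemar's chi-square test for dichotomous variables". Nothing is said about an incomplete pair, about therapist clustering or covariates in this step, or about whether 12-month scores or changes are compared.

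Three other parts of the Data Analysis section bear on it:

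- **Analytic Plans for Missing Data:** "All proposed analyses involving client outcome data will be carried out in Mplus, which provides full information maximum likelihood estimation". The same paragraph prefers this to listwise deletion.
- **Analytic Strategy to Account for Nesting Effects:** a standard model that ignores nesting "typically produces biased inferential tests because the error terms of units within each level are often correlated". The plan therefore uses multilevel modelling with a sandwich estimator.
- **Plan of Analysis for Main Outcomes: Aims 1 & 3, growth-model text:** the sandwich estimator is repeated for therapist nesting, and models are adjusted for demographics, income, caregiver education and site. The outcomes named there are symptoms together with executive and school functioning.

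**The concern.** A dependent t-test or McNemar's test, as normally run, needs both members of a pair. One missing outcome therefore also removes the observed outcome of the matched partner, which is a form of the deletion that the plan argues against. Neither test has a place for therapist. Yet medication use may well cluster by therapist and site: therapists in the Integrated condition guide the medication decision, and medication in the Behavioral Only condition follows site routine.

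There is a separate gap in confounding control. Executive and school functioning are outcomes and are measured at baseline, but they are not in the listed propensity variables. The paired tests, as described, do not adjust for the baseline value of the outcome being tested. The Aim 1 growth models represent baseline level through the intercept; the paired tests have no counterpart. If medication users and low or non-users differ at baseline in these domains after matching, the difference could be read as a medication effect.

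**Working it through.** **Inputs from the documents.** Sample size: "This comparative trial will randomly assign 140 adolescents with ADHD to Behavioral Only" or Integrated treatment, so 1:1 matching gives at most 140/2 = 70 pairs. Missing data: "we expect to have rates of missing assessment data on outcome variables between 10-15" percent. The plan gives no number of pairs, power, within-pair correlation, number of therapists or intraclass correlation for this question, so there is no stated figure to reproduce. What follows is illustrative.

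**Step 1: incomplete pairs.** Let d be the share missing. If losses are independent within pairs and occur after matching, the share of incomplete pairs is 1 − (1 − d)².

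- d = 0.10: 1 − 0.81 = 19%. Of 70 pairs, 70 × 0.81 = 56.7 remain.
- d = 0.15: 1 − 0.7225 = 27.75%. Of 70 pairs, 70 × 0.7225 = 50.6 remain.
- Observed clients discarded with a missing partner: 70 × 2 × d(1 − d) = 12.6 and 17.9, so about 13 to 18.
- Bounds: if partners are always missing together, 63 and 59.5 pairs remain; if never together, 56 and 49.

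**Step 2: precision cost of pair deletion alone.** Compare the complete-pair analysis with a likelihood analysis of the same matched clients that also uses the unpaired members. For two members with equal variance and correlation ρ, the ratio of standard errors is √[1 + (1 − ρ)d/(1 − d)].

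| ρ (assumed) | d = 0.10 | d = 0.15 |
|---|---|---|
| 0 | 1.054 | 1.085 |
| 0.2 | 1.043 | 1.068 |
| 0.4 | 1.033 | 1.052 |

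Pair deletion therefore makes the standard error about 3-5% larger at 10% missing and 5-9% larger at 15%.

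**Step 3: separating matching from missing data.** A larger penalty appears if the comparator is a regression on all observed clients. Assume 30% users: 42 users and 98 others. The variance ratio is [2(1 − ρ)/(42(1 − d)²)] / [(1/42 + 1/98)/(1 − d)], which equals 1.4(1 − ρ)/(1 − d).

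- With d = 0.10 to 0.15, the standard error is 25-28% larger at ρ = 0 and 12-15% larger at ρ = 0.2.
- With no missing data at all, it is already √1.4 = 1.18 (18% larger) at ρ = 0, and √1.12 = 1.06 (6% larger) at ρ = 0.2.

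Much of that penalty comes from leaving 98 − 42 = 56 non-users unmatched. The comparator also carries no variance cost for propensity adjustment.

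**Step 4: nesting.** Assume 16 to 32 therapists with equal caseloads and an intraclass correlation of 0.02 to 0.10. The design effect is 1 + (m − 1) × ICC, where m is clients per therapist. It runs from 1 + (4.375 − 1) × 0.02 = 1.07 to 1 + (8.75 − 1) × 0.10 = 1.77. A nominal 5% two-sided test would then run at about 6-14%. This is an upper range for these inputs, because it supposes that each therapist's clients all fall in the same use group.

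**Step 5: baseline values.** The propensity list names condition, demographics, ADHD severity and comorbid symptoms. Set against the outcome list, symptom status is covered; executive and school functioning are not. Site and therapist are not named either.

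**The case against.** - **The general rule may already govern.** The missing-data sentence covers every proposed client-outcome analysis, and a paired mean difference could be fitted by maximum likelihood in Mplus. Pair deletion is thus inferred from the tests named and is not stated. This stands. But the paragraph on Research Question 2 does not say that the tests will be fitted that way, whereas the Aim 1 and Aim 2 plans each restate maximum likelihood.
- **Some losses may precede matching.** Matching uses medication days at 12 months, and the caregiver interview is one source of those days. A client who misses that interview may never be matched unless therapist logs supply the figure, and then no partner is deleted. This stands, and it makes the 19-28% conditional.
- **Baseline status is partly handled.** A reader might infer that the tests ignore baseline functioning in breach of the plan's rules. The documents do not support that: baseline ADHD severity and comorbid symptoms are in the propensity model, and no rule requires adjustment for baseline functioning. The executive measure is described as capturing problems common in youth with ADHD, so matching on ADHD severity may also remove part of any gap.
- **The loss may be small.** A reader might attribute a 12-28% larger standard error to missing pair members. Step 3 shows that much of it comes from 1:1 matching. With 50% users assumed, the same comparison gives only −6% to +8%.
- **The question is secondary.** It is a non-randomized question under Aim 3. This stands.

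**Conclusion.** The conflict is real and can be read from the text: the tests named for Research Question 2, as conventionally run, follow neither the maximum-likelihood rule nor the sandwich-estimator rule. The omission of executive and school functioning from the propensity list is also real, but it is a gap in confounding control and not a breach of a stated rule.

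The size is modest where it can be given. At 10-15% missing, 19-28% of pairs would be incomplete, assuming independent losses after matching; the standard error rises by about 3-9% from pair deletion, assuming a within-pair correlation of 0 to 0.4. The effect of ignoring nesting depends on therapist numbers and an intraclass correlation that the documents do not give.

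Residual baseline bias cannot be sized. A reader might reach about 0.10 SD by multiplying a 0.2 SD residual gap by a 0.5 baseline-outcome correlation, but both inputs are assumed, and the plan does not say that follow-up scores rather than changes are tested. Nor does the point reach the randomized comparison. It deserves correction because the study intends to assess how medication decisions affect clinical outcomes, and families may read the result as a medication effect.

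**What to change.** Keep the propensity step and make these changes to the Research Question 2 text:

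1. Add baseline executive functioning, baseline school functioning and site to the propensity model.
2. Replace the paired tests with a regression, in Mplus, of the 12-month outcome on medication-use group in the matched or propensity-weighted sample. Use a logistic form for dichotomous outcomes. Include the baseline value of that outcome as a covariate, maximum likelihood for missing outcomes and therapist-clustered sandwich standard errors.
3. State how use days are obtained for clients who miss the 12-month interview, and report how many clients are left unmatched.

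The Aim 1 growth model should not simply be reused with a baseline covariate. It already contains baseline as a time point, so baseline would enter twice. It would also relate 3- and 6-month outcomes to medication days accumulated up to 12 months.

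Matching alone will still leave unmatched non-users out; weighting is the option that keeps them. The cost is revised SAP wording, modest re-programming with software and measures already planned, and the loss of the simple paired presentation.
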